The secondary objective is to compare the primary and secondary outcomes when stratified by stone size. This will allow us to explore the efficiency between Moses and thulium laser on treating large vs. small stones. Previous literature suggested that stone size was associated with operative time.^{ix} Patients will be separated based on the size of their stones: 3-10 mm or 11-20 mm and then randomized to holmium laser with Moses or thulium laser. Patients will be randomized into the groups by a ratio of 1:1.

Research Design and Methods

This study will be a randomized trial comparing ureteroscopy with laser lithotripsy with the Lumenis® Pulse™ P120H holmium laser system with the Moses technology (holmium laser with moses) versus the Soltive™ SuperPulsed Laser System with the thulium fiber laser technology (thulium laser). The primary objective is to compare the procedural time (minutes). We will keep strict timing from the minute the ureteroscope is inserted into the patient to the time the ureteroscope has been removed. The following information will be collected as secondary outcomes: (1) stone free rate; (2) total operative time (minutes); (3) fragmentation/dusting time (minutes, total time to fragment the stone, including the laser was in use and time of pedal pauses); (4) lasing time (minutes, time the laser was in use, not including pedal pauses); (5) total energy used (kilojoules, kJ); (6) laser efficiency (mm per minute); (7) number of times the laser pedals are pressed (left, right, and total pedal presses); (8) stone analysis; (9) complications; (10) quality of life survey (WISQOL short form) both pre-operatively and post-operatively and (11) physician evaluation of the laser. Physicians will complete a one page survey at the end of the case evaluating the laser (survey included as attachment). A total of 3 clinic visits (i.e., pre-operative visit, the stone surgery, and one post-operative visit) will be needed for this study. Stone parameters (i.e. size, location, Hounsfield units, presence of hydronephrosis, stone volume), demographic information, co-morbidities, and post-operative parameters will be collected from the medical record.

Number of Participants

NCT04963062
Protocol 2021-0695

Approximately 164 patients will be enrolled (see Data Analysis for sample size justification).

Inclusion Criteria

1. Patients at least 18 years of age, and less than 89 years old.

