If the patient is interested in the study, a member of the research team will approach him/her for enrollment. Consent process will be conducted face to face. Participants will be provided a written consent form in person. No waiting time is expected between informing the prospective participant and obtaining the consent.

Consent will take place during patients' pre-operative clinic visit. If patients are interested and there is not enough time to consent the patient in urology clinic, study information will be sent home with the patient and the patient will then be consented before their surgery in a private room (pre-operative room). Pre-operative room provides 1-1 1/2 hours of time. This should be ample time to conduct the consent process before surgery anesthesia.

All information about the study will be provided, and ample time will be made available for the participants to consider participation in the study.

Patient Randomization

Patients will be randomized (ratio 1:1) at the time of enrollment to be treated with either the holmium laser with Moses or the thulium laser. We will use Permuted Block Randomization (stratified by stone size 3 - 10 mm or 11-20 mm) (block size 4).

Study Procedures

1. The study team members review patients' medical record during patients' pre-operative clinic visit to see whether patients meet inclusion/exclusion criteria.
2. If patients meet the inclusion criteria, a study team member who is affiliated with the patient's clinical care (e.g., the surgeon) will initially approach the patients who are scheduled for laser lithotripsy treatment of urinary stones. (i.e., informed that there's a research study they may be eligible for, and asked if they want to learn more about it).
3. If the patient is interested in the study, a member of the research team will approach him/her for enrollment.
4. Patients will be asked to fill out a WISQOL short form at their pre-operative visit. This is standard of care for all stone patients in clinic.

5. Patients' total stone size (pre-operative CT) will be calculated and divided into two groups. Those with stones 3-10 mm and those with stones 11-20 mm. They will then be randomized to either the holmium laser with Moses or the thulium laser (randomization ratio 1:1) group.

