6. Patients will undergo stone surgeries with the laser that they are randomized to. A 200 micron fiber will be used with both machines. The patient's stone(s) will be treated in accordance with our routine clinical practice of fragmenting stone into small pieces (≤ 2 mm). One stone fragment will be collected for stone analysis if the patient does not already have a stone analysis on file (this is also standard of care). The faculty surgeons will perform all surgeries. We are unable to blind the surgeon to the laser used as the laser fibers and laser machines appear and sound different.
7. Procedural time as well as other information (see study design for the detail information) is collected.
8. After surgery, the patients will all have at least an abdominal x-ray within 1 month of surgery, if a CT scan has not already been completed(this is the standard of care). They will also be asked to fill out a WISQOL short form at their one-month follow up appointment. Otherwise, they will continue on our normal postoperative pathway. Postoperative complications will be collected.

Comparison of usual care and study procedures

Compared with our routine care, the only interventions imposed on subjects as a result of this study are (1) pre-procedural randomization to laser lithotripsy with either holmium laser with Moses or thulium laser, and (2) the use of patient & surgery information collected in describing our results. All the other activities are part of our routine clinical practice.

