Participation in the study will require a pre-operative CT abdomen without contrast, which is standard of care, as well as at least an abdominal x-ray post operatively which is also standard of care. Four surgeon will perform the ureteroscopy (i.e., [name], [name], [name], [name], and [name]). During surgery, patients' stones will be treated in accordance with our routine clinical practice of fragmenting stones into small pieces (<2 mm). Surgeons will use a 200 micron fiber for both the holmium laser with Moses and the thulium laser, but they will have the discretion to switch to a different fiber (ex. 150 micron thulium fiber) if they feel it is necessary during the case (if the surgeon changes the fiber during the surgery, the data will be analyzed separately). A stone fragment will be collected for stone analysis if the patient does not have one on file. This is our standard of care suggested by AUA guideline.^x All patients enrolled will undergo routine post-operative follow up including clinic appointments and imaging evaluation (with at least an abdominal x-ray). An abdominal x-ray is used for follow up of nephrolithiasis and provides significantly less radiation, and it is our routine care. However, if the patient already has a CT completed by the follow-up visit, an x-ray is not needed. WISQOL short form will be administered during the pre-operative appointment and at the post-operative appointment, which is standard practice in our clinic.

Withdrawal of participants

Patients can withdraw anytime. Once they decide to withdraw, they will continue their standard clinical care with us. We will continue to collect patients' information from patients' medical records for their routine medical care.

Study Intervention

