Since we have 5 surgeons participating in this study, we will use university-based cloud service (such as OneDrive) to temporarily save the enrollment log. Study team member will use their Net ID to access the enrollment log. The enrollment log is completely deidentified. Only participant ID (such as 101, 102) and the laser each participant is randomized to are saved in the enrollment log. Once we complete data collection, we will permanently delete it from the cloud.

Share of results

NCT04963062
Protocol 2021-0695

Some of the information collected for this study will go in the patient's medical record. This includes the results of the one-month post-operative image, stone analysis, stone surgery, and all clinic visits information as these are being conducted as standard of care. All other information from research specific procedures will NOT go in the patient's medical records.

We only publish aggregated results. No individual results will be shared. We will not share the data with outside institutions.

Economic burden to participants

This study does not place financial burden to patients. The study interventions are our routine clinical practice to treat stones. It will be same as they are not involved in this study.

The cost of the two laser treatments are equivalent.

Data Analysis

The data collected will be analyzed as an intention-to-treat analysis. Statistical analyses will include T-test and, if appropriate, Chi-square tests (e.g., for categorical data), and two-way MANOVA. Patient demographics and stone characteristics will be summarized as appropriate as continuous variables (mean and standard deviation) or categorical variables (frequency, percentage). To compare the two groups, continuous variables such as procedural time, total OR time, WISQOL etc., will be analyzed using T test and two-way MANCOVA (stratified by stone size 3 - 10 mm or 11-20 mm). The surgeon will be controlled as a covariate. Categorical variables such as stone free rate will be analyzed using chi-square.

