### **Data Analysis Plan**

Statistical analyses include using appropriate categorical/continuous and parametric/non-parametric statistical test. Patient demographics (such age, gender, race ethnicity) and stone characteristics (such as stone volume, location, density) will be summarized as appropriate as continuous variables (mean and standard deviation) or categorical variables (frequency, percentage). To compare the two groups, procedural time, laser time, ablation speed, ablation efficiency, total energy used, are analyzed using Wilcoxon test. The score of quality of life survey and laser evaluation survey are analyzed using MANOVA. Complication rate is analyzed using chi-square. Statistical significance is set as two-tailed p value < 0.05 and data are analyzed using SPSS 25.

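### The laser evaluation survey comes from four or five surgeons but is analysed with no surgeon term, so its p-value speaks only for those surgeons

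*Protocol*

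**What the plan says.** The protocol (Research Design and Methods) lists physician evaluation of the laser as the eleventh secondary outcome and describes how it is collected: "Physicians will complete a one page survey at the end of the case evaluating the laser". That is one form per case, and the planned enrolment is 164.

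The raters are a small, closed group. Study Procedures says "The faculty surgeons will perform all surgeries" and, of masking, "We are unable to blind the surgeon to the laser used". The number of raters is not consistent. Comparison of usual care and study procedures says "Four surgeon will perform the ureteroscopy" (followed by five name placeholders), while Date Management and Confidentiality says "Since we have 5 surgeons participating in this study".

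Patient Randomization allocates patients 1:1 in blocks of four, stratified by stone size and not by surgeon. Each surgeon can therefore be expected to rate both lasers many times.

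On analysis, the SAP (Data Analysis Plan) says "The score of quality of life survey and laser evaluation survey are analyzed using MANOVA", with a two-tailed 0.05 threshold. It names no surgeon term, random effect or per-surgeon summary. The protocol's Data Analysis section does plan surgeon as a covariate, in a MANCOVA for continuous variables. Its examples are procedural time, total OR time and WISQOL, followed by an open-ended etc. The laser survey is not among them, and the SAP does not repeat the covariate.

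**The concern.** MANOVA without a surgeon term treats about 164 forms as 164 independent opinions, when four or five people supply them all.

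The feature that matters is narrow. Surgeons who are simply strict or generous raters do little harm, because each uses both lasers and their general level largely cancels from the comparison. The difficulty arises if surgeons differ in which laser they prefer. That is plausible for subjective, unblinded ratings when one laser is in current use and the other has so far been used only on trial (protocol, Study Intervention). The average preference then depends on which few surgeons took part, and more cases per surgeon do not remove that uncertainty.

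At stake is the wording of the conclusion. A significant result could be reported as surgeons preferring one laser, when the analysis supports only a statement about the participating surgeons.

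**Working it through.** **The plan's own figure.** The sample size concerns procedural time. With a difference of 4.6 min, SD 6.5 and 33 per group, exact t-test power is 0.808, which matches the stated 80%. Then 33 × 1.25 = 41.25, taken as 41, and 4 stratum-by-arm cells × 41 = 164. No power or error rate is stated for the survey, so only the row count carries over.

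**Inputs.** From the documents: 164 cases, four or five surgeons, 1:1 allocation by patient, two-sided alpha 0.05. Assumed: 5 surgeons with 32 ratings each (160 rows; 164/5 = 32.8), a single score with residual SD 1, and a surgeon-to-surgeon SD of laser preference, τ, of 0.3, 0.5 or 0.8. The documents give no τ.

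**Step 1: variance of the laser contrast.** If the target is surgeons in general, the variance is τ²/5 + 4/160. The independent-ratings test counts essentially only 4/160 = 0.025. The hand error rate below is 2 × [1 − Φ(1.96/√ratio)].

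| τ | τ²/5 | Total variance | Ratio to 0.025 | Effective ratings (160/ratio) | Hand error rate |
|---|---|---|---|---|---|
| 0 | 0 | 0.025 | 1.0 | 160 | 5% |
| 0.3 | 0.018 | 0.043 | 1.72 | 93 | 13% |
| 0.5 | 0.050 | 0.075 | 3.0 | 53 | 26% |
| 0.8 | 0.128 | 0.153 | 6.1 | 26 | 43% |

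The hand rates run slightly high because differing preferences also raise the estimated residual variance a little.

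**Step 2: simulation, surgeons drawn from a population with no average preference.** Type I error is about 11–13%, 19–25% and 35–39% at τ = 0.3, 0.5 and 0.8. With surgeon as an additive covariate it is about 13%, 24% and 39%, so the covariate is no remedy.

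A separate simulation with 164 cases randomised by patient, and the surgeon main effect at 20% of rating variance, set the preference share at 2%, 5% and 10%. In residual SDs these shares are √(4 × 0.02)/√0.78 = 0.32, √(4 × 0.05)/√0.75 = 0.52 and √(4 × 0.10)/√0.70 = 0.76. Error was 11.8%, 23.4% and 36.9% unadjusted, and 13.5%, 25.8% and 40.9% with the covariate. With four surgeons the unadjusted rates were 15.8%, 25.3% and 38.6%. With no preference variation, a surgeon main effect of 20–40% of variance left the error at about 5%.

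**Step 3: joint test of several items.** In the same setting, a two-group MANOVA on three items correlated 0.5 gave 5.6%, 17.8%, 40.7% and 62.9% at shares of 0, 2, 5 and 10%. This is illustrative only, since the survey's items and scoring were not available.

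**Step 4: the same design with the five surgeons fixed.** Preferences differ but average zero across these five. Error of the independent-ratings test is 5.0%, 4.6% and 4.1% at τ = 0.3, 0.5 and 0.8, and with the covariate 5.2%, 4.1% and 3.8%. For a claim confined to these surgeons there is no inflation.

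**Step 5: price of generalising.** A one-sample t-test on five surgeon-specific differences (4 df) held the error at 4.4–5.7% in the five-surgeon settings of the separate simulation in Step 2. Its 95% half-width is 2.776 × √(total variance) = 0.58, 0.76 and 1.09 residual SDs, against about 0.31 for the independent-ratings analysis. Its power for a 0.5-SD difference is about 45%, 29% and 17%.

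**The case against.** The strongest reply concerns the target of inference. This is a single-department trial with a fixed group of faculty surgeons, and neither document claims to speak for surgeons in general. For these surgeons the caseload-weighted average preference is a real quantity, and Step 4 shows that the planned type of test does not over-reject for it. This stands. A reader might infer that the false-positive rate is simply well above 5%; the documents do not support that without the condition that the conclusion is extended beyond the participants. What remains is that neither document states the limit, and the planned analysis would not show whether the surgeons disagree.

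A reader might also infer that the effective sample is only four or five. That is too strong: on the assumed values it is about 93, 53 or 26 ratings. The number of surgeons governs the degrees of freedom, and becomes the effective sample only as preference variation dominates.

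Third, the protocol does plan a surgeon covariate, and its etc. could be read to include the survey. It would be wrong to say that the plan ignores surgeon. But the SAP sentence that names the survey drops the term, and an additive term would not address differing preferences.

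Finally, the preference variance is assumed, the survey form is an attachment that was not seen, and this is one of eleven secondary outcomes. All true. They limit the size and weight of the point but do not remove it.

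**Conclusion.** The point holds in a limited form. The SAP's survey analysis has no surgeon term although four or five unblinded surgeons supply every rating. If their laser preferences differ, significance at 0.05 supports a statement about their own caseload-weighted average. Extended to surgeons in general, the same test would have a type I error of about 11–13%, 19–25% or 35–39% at assumed preference SDs of 0.3, 0.5 or 0.8 residual SDs, and 5% at zero. These figures assume five surgeons with equal caseloads and a single score. They show what could happen; they do not estimate what will. The primary procedural-time result is not affected by this point.

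**What to change.** In the SAP:

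- Analyse the laser survey separately from the quality-of-life MANOVA, with surgeon and laser-by-surgeon terms.
- Report the thulium-minus-Moses difference for each surgeon, with its interval and number of cases.
- State that the conclusion is limited to the participating surgeons.
- If a claim beyond them is wanted, use a random laser-by-surgeon effect with small-sample degrees of freedom and label it descriptive. Four or five raters give a wide interval and low power (Step 5), so this should not be the main analysis.

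In the protocol, reconcile the surgeon count between Comparison of usual care and study procedures (four) and Date Management and Confidentiality (five), and say whether the surgeon covariate in Data Analysis is meant to cover the survey.

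The cost is SAP and protocol wording, a narrower claim and slightly more reporting. No new data are needed as long as the operating surgeon is recorded for each case, which the protocol's own covariate already requires.

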2. Patients with renal or ureteral urinary stones who require endoscopic treatment in the outpatient operating room
3. Patients' stone size in a single renal unit of 3-10 mm and 11-20 mm. Stone size is defined as the largest diameter of a single stone on pre-operative CT. Patients with multiple stones will be included as long as their largest stone size falls within the above parameters.

Exclusion Criteria

1. Patients under 18 years of age and over 89 years old.
2. Pregnant patients
3. Patients with transplant kidneys
4. Patients with irreversible coagulopathy
5. Patients with known ureteral stricture disease
6. Patient who do not have a pre-operative CT.
7. Non-English speaking, vulnerable patients such as lacking of decision-making capability, prisoner, adult unable to consent, will not be enrolled.

Recruitment methods

Patients who are to be scheduled for laser lithotripsy treatment of urinary stones as outpatients will be approached for study participation. During patients' pre-operative clinic visit, eligibility screening (by reviewing patients' medical record that is relevant for inclusion/exclusion criteria) will occur before recruitment. If patients meet the inclusion criteria, they will be initially approached by a study team member who also works in the urology clinic (i.e., the surgeon informs the patient that there's a research study they may be eligible for, and asked if they want to learn more about it).

No other recruitment materials will be used in this study. Holmium laser with Moses or thulium laser to treat stones is our routine care. Patients have been informed about the laser lithotripsy treatment before they schedule their surgery. We will only recruit patients from the outpatient OR, so this will not include patients who come in emergently through the Emergency Department.

NCT04963062
Protocol 2021-0695

No compensation will be provided to participants.

Consent Process

A study team member who is affiliated with the patient's clinical care (e.g., the surgeon) will initially approach the patients who are scheduled for laser lithotripsy treatment of urinary stones. (i.e., informed that there's a research study they may be eligible for, and asked if they want to learn more about it).

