We plan to enroll 164 patients in this study. Patients will be stratified into two groups according to their stone size (3-10 mm or 11-20 mm) and then randomized to either holmium laser with Moses or thulium laser. The stone size is defined as the largest stone size (largest diameter on pre-operative CT), if patients have multiple stones. Previous literature suggested stone size is associated with operative time.^{ix} A significance level of 0.05 will be used with a two-sided two-sample equal-variance t-test. Group sample sizes of 33 and 33 achieve 80% power to detect a significant difference between the means when the mean difference is 4.6 minutes with a standard deviation of 6.5 minutes. We also decide to increase the sample size by 25% (41 patients per group). This will allow for the possibility that the randomization scheme is intra-operatively abandoned for some reason (e.g., equipment failure), that the planned procedure was unable to be completed for some reason, as determined by the surgeon in

charge of the case, and/or that the patient – after his/her procedure – wishes to withdraw from the study and exclude his/her information from our analysis.

ⁱ Scales CD Jr, Smith AC, Hanley JM, Saigal CS; Urologic Diseases in America Project. Prevalence of kidney stones in the United States. *Eur Urol*. 2012 Jul;62(1):160-5.

ⁱⁱ Geraghty RM, Jones P, Somani BK. Worldwide Trends of Urinary Stone Disease Treatment Over the Last Two Decades: A Systematic Review. *J Endourol* 2017 Jun;31(6):547-556.

ⁱⁱⁱ Assimos D, Krambeck A, Miller NL, et al: Surgical Management of Stones: American Urological Association/Endourological Society Guideline, PART II. *J. Urol.* 2016.

^{iv} Andreeva V, Vinarov A, Yaroslavsky I, et al. Preclinical comparison of superpulse thulium fiber laser and a holmium:YAG laser for lithotripsy. *World J Urol*. 2020 Feb;38(2):497-503.

^v Ventimiglia E, Doizi S, Kovalenko A, et al. Effect of temporal pulse shape on urinary stone phantom retropulsion rate and ablation efficiency using holmium:YAG and super-pulse thulium fibre lasers. *BJU Int*. 2020 Jul;126(1):159-167.

^{vi} Bagrodia A, Gupta A, Raman JD, et al. Predictors of cost and clinical outcomes of percutaneous nephrolithotomy. *J Urol*. 2009 Aug;182(2):586-90.

^{vii} Schuster TG, Hollenbeck BK, Faerber GJ, Wolf JS Jr. Complications of ureteroscopy: analysis of predictive factors. *J Urol*. 2001 Aug;166(2):538-40.

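### Stone location and density are recorded at baseline but left out of the comparison of procedural time; adjusting for both would gain precision, mainly within the size bands

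*Protocol*

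**What the plan says.** - **Population.** Inclusion criterion 2 of the protocol admits "Patients with renal or ureteral urinary stones who require endoscopic treatment in the outpatient operating room". Both locations enter one comparison.
- **Endpoint.** Under Research Design and Methods, procedural time is clocked from scope in to scope out. It therefore covers reaching the stone as well as breaking it.
- **Data held.** The same section lists "Stone parameters (i.e. size, location, Hounsfield units, presence of hydronephrosis, stone volume" among the items taken from the medical record. Patients without a pre-operative CT are excluded, so location and density should be known for everyone before surgery.
- **Randomisation.** Permuted blocks of 4, stratified by stone size (3–10 or 11–20 mm) and by nothing else.
- **Protocol, Data Analysis.** A t-test and a two-way MANCOVA by size band, with surgeon as the only named covariate.
- **SAP, Data Analysis Plan.** A Wilcoxon test of procedural time with no stratum or covariate. Location and density appear only in the descriptive part: "stone characteristics (such as stone volume, location, density) will be summarized".
- **Sample size (protocol, Data Analysis).** "A significance level of 0.05 will be used with a two-sided two-sample equal-variance t-test"; "Group sample sizes of 33 and 33 achieve 80% power" when "the mean difference is 4.6 minutes with a standard deviation of 6.5 minutes". The protocol then inflates this by 25% to 41 per group and plans 164 patients.

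**The concern.** The plan accepts that a baseline factor related to operating time should be handled: it stratifies by size for that reason and controls for surgeon. Location and density plausibly act in the same way. A ureteral and a renal stone of equal size can differ in scope time because of access, and a denser stone may take longer to break. Neither difference is due to the laser. Left unadjusted, this variation stays in the residual SD, widens the confidence interval and lowers power.

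If location turned out unbalanced between lasers, an adjustment chosen after seeing the data would be open to challenge. Prespecifying it avoids that dispute.

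**Working it through.** **Inputs from the protocol:** difference 4.6 min, SD 6.5 min, two-sided 0.05, 33 per group before and 41 after inflation, 164 in total. Since 164 = 4 × 41, there are 41 per laser within a size band and 82 per laser overall.

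**Assumed, because the documents give no figure:** ureteral share q = 0.3 to 0.5; gap in mean scope time between locations D = 5, 10 or 15 min; share of variance explained by location and density R² = 0.10 to 0.30. The SD of 6.5 is used both overall and within a band.

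**1. The plan's own figure.** Exact noncentral-t power is 79.6% at 32 per group and 80.8% at 33, so 33 reproduces. 33 × 1.25 = 41.25, stated as 41. With SD 6.5, power is 88.6% at 41 and 99.5% at 82.

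**2. Case A: 6.5 min already includes location and density.** Residual SD = 6.5 × √(1 − R²). 95% CI half-width = t × SD × √(2/n), with t = 1.975 at 82 per laser and 1.990 at 41. The few degrees of freedom spent on covariates are ignored.

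| R² | Residual SD | Half-width, 82 per laser | Half-width, 41 per laser |
|---|---|---|---|
| 0 | 6.50 | 2.00 | 2.86 |
| 0.10 | 6.17 | 1.90 | 2.71 |
| 0.30 | 5.44 | 1.68 | 2.39 |

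Planned power is intact here. Adjustment raises it at 41 per laser from 88.6% to 91.6% (R² 0.10) or 96.6% (R² 0.30).

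**3. Case B: 6.5 min is the SD within a location.** Unadjusted SD = √(6.5² + q(1 − q)D²). For example, with q = 0.5 and D = 10: √(42.25 + 25) = 8.20. Ranges run over q = 0.3 to 0.5.

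| Gap D | Unadjusted SD | Power, 82 per laser | Power, 66 per laser | Power, 41 per laser (one band) |
|---|---|---|---|---|
| 5 min | 6.89–6.96 | 98.8–98.9% | 96.5–96.8% | 84.0–84.7% |
| 10 min | 7.95–8.20 | 94.6–95.7% | 89.2–91.0% | 70.9–73.5% |
| 15 min | 9.46–9.92 | 83.9–87.2% | 75.3–79.2% | 54.5–58.5% |

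The 66 column (2 × 33) is the overall comparison if the whole 25% allowance is lost.

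**4. Chance imbalance.** The SD of the between-arm difference in ureteral share is √(2q(1 − q)/n). At q = 0.5 and 82 per laser this is √(0.5/82) = 0.078, so the 95% range is ±15 points. At D = 10 that shifts the unadjusted difference by up to 1.5 min, against a target of 4.6 min. This is the same variance as in step 3 seen from another side, not a further loss.

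**The case against.** **The primary comparison is well powered.** A reader might infer from a calculation at 33 per arm that the primary result has only 46–64% power for gaps of 10–15 min. The documents do not support that. The primary objective is the laser-against-laser comparison, which has 82 per laser; comparison by stone size is the secondary objective. Overall power stays above 80% except when the largest assumed gap is combined with loss of the full allowance. This objection stands and sets the size of the point.

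**The SD may already be a mixed-population figure.** The protocol gives no source for 6.5 min and does not call it a within-location SD. If it describes the mixed population to be enrolled, Case A applies and there is no shortfall. This stands too; adjustment would then be a gain rather than a repair.

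**Imbalance is not bias.** A reader might infer that pooling the two locations biases the result. Randomisation keeps the comparison unbiased on average, and chance imbalance is already counted in the standard error.

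**Every effect size is assumed.** The documents name only stone size as associated with operating time. No magnitude can be put on density alone, which is why the results are ranges.

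**Other time measures help.** Fragmentation and lasing times are recorded separately and depend less on access. They are secondary, however, and do not sharpen the primary endpoint.

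**Fragment retrieval.** The protocol says "One stone fragment will be collected for stone analysis if the patient does not already have a stone analysis on file". A reader might infer that retrieval lengthens the clock for those patients alone. The documents do not say when or how the fragment is taken, how long it takes or how many patients need it. Even 3–5 min in half of patients would leave 96–98% power at 66 per laser.

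**The t-test power is not the Wilcoxon power.** True, but the difference is small if times are near normal: taking 95.5% relative efficiency, about 87.0% against 88.6% at 41 per laser with SD 6.5.

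**Conclusion.** The point holds as one of precision. Two baseline variables that every patient should have, and that plausibly drive scope time, are described but used in no comparison.

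Under Case A (10–30% of variance explained), the gain is 0.10–0.32 min off an overall half-width of 2.00 min. Under Case B, the primary comparison loses little at a 5 or 10 min gap. The comparisons within a size band, on which the 41-per-group figure appears to be built, fall to about 71–73% at 10 min and 55–59% at 15 min. Which case applies cannot be settled from the documents.

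The absence of these covariates does not invalidate the test, and it does not show that randomisation needed a further stratification factor.

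**What to change.** In the SAP, make the primary analysis of procedural time a prespecified covariate-adjusted model: ANCOVA, on the log scale or rank-based if times are skewed, with terms for laser, size stratum, surgeon, location (renal or ureteral) and Hounsfield units. Keep the unadjusted Wilcoxon test as a sensitivity analysis. State the rule for choosing the scale, and how patients with stones in both locations are classified, before outcome data are examined. A yes/no term for a stone analysis already on file is optional.

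This is more than a change of wording: a Wilcoxon test takes no covariates, so the SAP's primary test is replaced. The same edit can reconcile the SAP with the protocol, whose size stratum and surgeon covariate the SAP omits.

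Cost: location and Hounsfield units take one degree of freedom each beyond what the protocol already specifies, and the optional term one more. No new data and no change to randomisation are needed.
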